### 3. ***Subject Recruitment and Screening:***

Subjects will accrue to the study when initiating a new line of systemic cancer therapy (ie, intravenous chemotherapy or immunotherapy). Subject recruitment and screening will occur pragmatically via weekly queries of upcoming Epic/Beacon treatment plans, identifying patients scheduled to initiate a new line of systemic cancer therapy in the following week.

Given the pragmatic nature of this study and its objective to test implementation strategies to promote engagement in an evidence-based practice in routine cancer care, ***we are requesting a waiver of informed consent***. There are several reasons to justify this request. First, we are assessing the impact of implementation strategies delivered to patients through adjustments in existing clinical workflows using the electronic medical record and other patient communication tools. Second, it would not be feasible to consent every patient enrolled in the trial. Third, individual informed consent might impact patient behavior, thereby complicating the study design and interpretation of its findings. Fourth, none of the proposed strategies forces behavior change. No one will be coerced or forced to engage in PRO monitoring; rather, the goal of nudges is to promote evidence-based practices while preserving autonomy and freedom of choice.

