**2. Study Duration:**

The study duration will be approximately 6 months, including a 3-month accrual period and 3-month follow-up period per participant over which primary outcomes will be ascertained.

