**4. Subject Follow-up:**

Subjects will be followed for approximately 3 months after enrollment.

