**STUDY PROCEDURES:**

**1. Detailed Description:**

Eligible patients will be identified pragmatically using the criteria listed above, and will be independently randomized to study arms using a three-arm design. A description of the three study arms follows:

- (1) Usual practice.** This arm will consist of encounter-based PRO monitoring, in which patients have an opportunity to complete PRO questionnaires via patient portal in advance of clinical encounters or via tablet during clinical encounters. While clinicians will be encouraged to view and discuss PROs with patients during clinical encounters, they will not be prompted to do so in real-time, nor will there be alerts for escalating symptoms.
- (2) Encounter-based PRO monitoring plus patient reminders and triage nurse alerts.** This arm consists of usual practice (described above) plus the addition of patient reminders to complete PRO questionnaires and triage nurse alerts for severe symptoms. Patient reminders will be operationalized through the Epic patient portal. Triage nurse alerts will be routed to Epic symptom management pools in response to a patient reporting moderate or severe symptoms. Patients will have the opportunity to decline or opt-out of triage nurse support. Clinical interventions stemming from triage nurse alerts will be up to the discretion of clinical teams – ie, clinical responses will be neither prescriptive nor mandatory. Notably, the entry point for triage nurse alerts (ie, Epic symptom management pools), as well as resultant clinical responses, are existing standard operating procedures/practices for patients reporting symptoms by phone.
- (3) Remote PRO monitoring plus patient reminders and triage nurse alerts.** This arm will consist of weekly PRO questionnaires administered via the patient portal, de-linked from clinical encounters. Patient reminders and triage nurse alerts will be operationalized as described in Arm (2).

We will use rapid cycle approaches (RCA) to optimize implementation strategies to ensure face validity and maximum effect. We will focus on optimizing content, messaging, and design. RCA procedures will involve design meetings with study team, discussions with administrators and clinicians who are members of our Implementation Lab, as well as piloting of nudges with potential participants to elicit feedback.

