**Aim 1**

The primary outcome will be PRO adherence, measured at the patient level as the proportion of expected PRO questionnaires completed per patient. Secondary specifications will include:

- % patients completing at least one PRO questionnaire during study period
- % patients completing at least one PRO questionnaire per month during the study period

Secondary implementation outcomes will include:

- % patients with at least one note documenting PROs during study period
- % patients with at least one note documenting PROs per month during study period
- For Arms 2-3 only: time to alert response

Secondary effectiveness outcomes will include:

- Symptom burden, measured as a composite and for each PRO/symptom
  - a. For Arms 2-3 only: % patients who trigger alert
- Acute care utilization, measured as % patients with ED visit or hospitalization
- Treatment delays/modifications, measured as % patients with treatment delay/modification
- Duration of therapy

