### **5. Statistical Analysis:**

#### **Aim 1**

The design is a three-arm randomized trial, resulting in three independent study arms: (1) usual practice, (2) encounter-based PRO monitoring with patient reminders and triage nurse alerts, (3) remote PRO monitoring with patient reminders and triage nurse alerts. Implementation and effectiveness outcomes will be assessed across arms. The main comparison for the purposes of power calculations will be Arm 2 vs Arm 1. Multivariable linear regression will be used to model patient PRO adherence as a function of nudge exposure (i.e., study arm assignment). Covariates will be assessed across study arms and included in the model if unbalanced across arms.

Significance will be determined using the z-score corresponding to each of the estimated effects, using a two sided type 1 error of 5%. All enrolled patients will be included in the intention-to-treat analysis.

The secondary outcomes will be similarly modeled except using logistic models as appropriate for binary outcome variables. All hypothesis tests will use a two-sided alpha of 0.05 as the threshold for statistical significance.

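### Duration of therapy and time to alert response fall by implication to linear regression, with no rule for courses still ongoing at 3 months or alerts without a response time

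*Combined protocol and SAP*

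**What the plan says.** Statistical Analysis, Aim 1, sets the primary model: "Multivariable linear regression will be used to model patient PRO adherence as a function of nudge exposure". It then deals with every secondary outcome in one sentence: "The secondary outcomes will be similarly modeled except using logistic models as appropriate for binary outcome variables". Logistic regression for binary outcomes is the only stated exception. The same section puts every enrolled patient into the intention-to-treat analysis.

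Data Collection, Aim 1, lists two secondary outcomes measured on a time scale: "Duration of therapy" among the effectiveness outcomes, and "For Arms 2-3 only: time to alert response" among the implementation outcomes.

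On observation time, Subject Recruitment and Screening says "Subjects will accrue to the study when initiating a new line of systemic cancer therapy", and Subject Follow-up says "Subjects will be followed for approximately 3 months after enrollment". Study Duration describes a "3-month follow-up period per participant over which primary outcomes will be ascertained" and gives no longer window for secondary outcomes.

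On alerts, the Detailed Description lets patients decline triage nurse support. Appendix 1 ends with a yes/no item asking Arms 2 and 3 whether they want the nurse team to contact them. Arm 3 questionnaires are weekly.

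The documents give no start, stop, censoring or death rule for duration of therapy, no definition of an alert response, and no survival or restricted-mean method for either outcome. Hazard ratios are mentioned once, under Aim 2, for effect modification on PRO adherence.

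**The concern.** A linear model needs a number for every record. A patient still on treatment at month 3 has no observed duration, and an alert nobody answered has no response time. The analyst must drop such records or assign a value, and the plan does not say which. The choice matters:

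- Dropping ongoing courses compares only patients who stopped within 3 months. That conditions on the outcome and removes most of any effect on duration.
- Entering 3 months for each ongoing course keeps everyone and estimates a sensible quantity, but that quantity is time on therapy within 3 months, not full duration.
- Comparing only answered alerts compares speed among responders. It cannot detect that one arm leaves more alerts unanswered.

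The unit of analysis for alerts is also open. An Arm 3 patient can trigger several alerts, and treating these as independent understates the standard error.

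Both outcomes are secondary. Even so, this is a hybrid type 2 design meant to evaluate effectiveness as well as implementation, and alert response time is a direct measure of the nurse component. The handling rule should not be chosen after the data are seen.

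**Working it through.** The plan gives no power or variance figure for either outcome (its one power statement concerns PRO adherence), so there is no stated figure to reproduce. The sizes below rest on assumptions, marked as such.

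**Inputs from the documents.** 480 patients randomised 1:1:1 gives 480/3 = 160 per arm. Follow-up is 3 months. Two-sided alpha is 0.05. Power and Sample Size gives a mean of about 3 questionnaire opportunities per patient. Weekly administration over 3 months gives about 13.

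**A. Duration of therapy.** Assumptions: exponential durations, hazard ratio 0.6, and 70% or 50% of usual-practice patients still on therapy at month 3. With S the share on therapy at month 3, the hazard is -ln(S)/3 and the restricted mean is (1 - S)/hazard.

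- *70% on therapy.* Hazards are 0.1189 and 0.6 x 0.1189 = 0.0713. The comparison arm has 0.7^0.6 = 0.807 on therapy. Restricted means are 0.300/0.1189 = 2.52 and 0.193/0.0713 = 2.70 months, a difference of 0.18. With SDs of 0.87 and 0.72, SE = sqrt((0.87^2 + 0.72^2)/160) = 0.089, z = 0.177/0.089 = 1.99, and power is about 51%. Log-rank: expected events 160 x 0.300 + 160 x 0.193 = 78.8, |ln 0.6| x sqrt(78.8)/2 = 2.27, and power is about 62%.
- *50% on therapy.* The same steps give restricted means of 2.16 and 2.45 months, a difference of 0.29, SE 0.109 and power about 76%. Log-rank, with 134 expected events, has about 84%.

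Simulation of the same scenarios (2,000 runs, Monte Carlo error about 1 point) agrees:

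| On therapy at month 3 (usual practice) | Ongoing courses dropped | Ongoing set to 3 months | Log-rank |
|---|---|---|---|
| 70% | 6% | 53% | 62% |
| 50% | 7% | 77% | 85% |

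A separate set of assumed medians (3 vs 4.5, 4 vs 6 and 6 vs 9 months) shows the same pattern: 4-6% with ongoing courses dropped, 35-60% with the cut-off entered, 44-68% with log-rank. Even log-rank is limited, because 3 months of follow-up yields few events.

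**B. Unanswered alerts.** Assumptions: 48 to 112 alerted patients per arm, one alert each, equal speed among responders (mean 24 hours), and a response within 7 days for about 80% vs 60% or 90% vs 70%. Comparing mean times among responders rejects in 5-6% of runs, which is the error rate. Log-rank with unanswered alerts censored rejects in 53-93%.

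**C. Several alerts per patient.** Assumptions: 40% of questionnaires trigger an alert, all are completed, about 3 opportunities in Arm 2, and ICC 0.1 to 0.3. Alerts per patient are 3 x 0.4 = 1.2 in Arm 2 and 13 x 0.4 = 5.2 in Arm 3. The design effect is 1 + (m - 1) x ICC.

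- Naive variance is proportional to 1/(160 x 1.2) + 1/(160 x 5.2) = 0.00521 + 0.00120, so Arm 2 contributes 81.25% and Arm 3 18.75%.
- ICC 0.1: 0.8125 x 1.02 + 0.1875 x 1.42 = 1.095. The SE ratio is 1/sqrt(1.095) = 0.956, or 4% too small.
- ICC 0.3: 0.8125 x 1.06 + 0.1875 x 2.26 = 1.285. The SE ratio is 1/sqrt(1.285) = 0.882, or 12% too small.

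If alert counts vary binomially between patients, the design effects become 1 + 0.8 x ICC and 1 + 4.8 x ICC, and the shortfall is 7-17%. With 60% of questionnaires completed (assumed) and varying counts it returns to 4-12%.

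**The case against.** The strongest reply is that the text already points to an acceptable analysis. A reader might infer from the 6-7% row that linear regression will erase a real effect on duration. That requires dropping everyone still on therapy, and the section's intention-to-treat sentence argues against it. If all patients are kept, the natural linear analysis is the 3-month restricted mean, which is valid when each patient is observed for the full window. The gap to log-rank is then modest, on outcomes the trial was not sized for. This stands, and it sets the scale of the point. It does not supply the missing rule, because saying that a patient is included does not say what number an unfinished course receives.

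A reader might also take "clinical responses will be neither prescriptive nor mandatory" as showing that alerts will go unanswered. In context it concerns the clinical interventions that follow an alert, not whether a nurse handles it, and the same paragraph describes the alert pools and responses as existing practice. How many alerts will lack a time is unknown. The better documented route is the patient who declines nurse support. Such a patient is not a slow responder, and censoring that alert as if contact were pending would be wrong.

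Finally, weekly questionnaires might suggest standard errors 16-33% too small. That is Arm 3 alone (1/sqrt(1.42) = 0.84 and 1/sqrt(2.26) = 0.67). The comparison is Arm 2 with Arm 3, and Arm 2 carries most of the variance with little clustering. Nothing in the plan says that alerts would be separate records.

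Linear regression is also never named for these two outcomes. It follows only from the phrase about similar modelling.

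**Conclusion.** The point holds as an incomplete specification of two secondary outcomes. By implication both go to linear regression with no rule for incomplete values.

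For duration of therapy, the likelier cost is about 8 to 10 power points against log-rank, and an estimate that should be labelled as time on therapy within 3 months. Near-total loss of power would occur only in a complete-case analysis, which the plan does not state and its intention-to-treat sentence argues against.

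For alerts, an analysis of answered alerts alone can miss a difference in response. If alerts are the unit, the standard error would be about 4-12% too small.

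All sizes depend on assumed durations, response rates, alert frequency and ICC, because the documents give none. The direction of the complete-case problem does not depend on the particular values. The primary outcome is untouched, so this should be fixed but does not threaten the trial's main conclusion.

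**What to change.** Add to Statistical Analysis, Aim 1:

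- **Duration of therapy.** Define start and end. Analyse as time to discontinuation, with ongoing courses censored at 3 months and death counted as the end of therapy, by Cox model or log-rank test. Alternatively, use a 3-month restricted mean that keeps every randomised patient, and label it so.
- **Time to alert response.** Define what counts as a response and when the clock starts. Analyse as time to event, with unanswered alerts censored at a fixed cut-off. Report alerts where the patient declined outreach separately, not as pending. Use the first alert per patient, or standard errors clustered by patient.

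The cost is a few sentences and a little more analysis work. No new patients or follow-up are needed.

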## **BACKGROUND:**

Routine PRO monitoring is an evidence-based practice that improves patient outcomes. Patients with cancer commonly experience symptoms which go unrecognized by clinical teams up to half of the time. PROs are a powerful tool to bridge this gap, amplifying the patient experience and improving communication between patients and clinicians. Basch et al. conducted a seminal clinical trial in which weekly PRO symptom assessments with care team alerts led to reduced care utilization, improved quality of life, and lengthened overall survival among patients receiving active treatment for advanced solid tumors. Subsequent randomized trials have corroborated the quality of life and survival advantages of PRO monitoring in other cancer populations and practice settings.

Real-world adherence to PRO monitoring is lower than in seminal clinical trials, with potential racial/ethnic disparities. Multilevel barriers to PRO implementation exist at the patient, clinician, practice, and system levels. While patient adherence to PRO monitoring in seminal trials ranged from 70 to 90 percent, real-world adherence is much lower and more variable. Our preliminary research (under review) demonstrates that in a large, multi-site rollout of PRO monitoring, mean patient-level adherence was less than 50 percent. Moreover, compared to non-Hispanic White patients, Black and Hispanic patients were 9% and 4% less likely to complete PRO questionnaires, respectively, but more likely to report more severe symptoms. These results highlight that historically marginalized subgroups may benefit less from current methods of PRO administration, potentially reinforcing existing disparities in symptom management if not remediated.

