**METHODS:**

**1. Study Instruments:**

We do not anticipate the use of study instruments beyond the PRO questionnaire **[Appendix 1]**, which is already administered in routine practice. Any additional study instruments will be submitted to the IRB as a modification prior to use.

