**2. Data Collection:**

The electronic medical record and other Penn Medicine secondary databases used to collect data in routine care will be used to collect information on study participants. We will also collect data from the U.S. Census via publicly available datasets.

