### **Aim 2**

Aim 2 measures, collected through the electronic medical record and using publicly available U.S. Census data, will include:

- *Patient-level data*: age, sex, race/ethnicity, education, marital status, cancer type, cancer stage, health insurance (e.g., Medicare, Medicaid, commercial);
- *Clinician-level data*: years in practice and patient panel size;
- *Practice-level data*: setting (community vs. hospital-based), urban vs. non-urban location, and health insurance mix;
- *Ecologic-level data* linked at the patient- and practice-level, including median income and educational attainment.

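### The imbalance rule would leave a pre-randomization symptom score out of the symptom-burden model whenever that score is balanced, and no section plans to extract it where it exists

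*Combined protocol and SAP*

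**What the plan says.** The Data Collection section (Aim 1) lists four secondary effectiveness outcomes: symptom burden, acute care use, treatment delay or modification, and duration of therapy. The first is defined as "Symptom burden, measured as a composite and for each PRO/symptom". No time point or summary over follow-up is given.

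The Statistical Analysis section (Aim 1) models the primary outcome by linear regression on study arm and adds this rule: "Covariates will be assessed across study arms and included in the model if unbalanced across arms". For the rest it says: "The secondary outcomes will be similarly modeled except using logistic models as appropriate for binary outcome variables". No covariate is named.

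Four other places bear on whether a baseline symptom score exists:

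- Study Instruments describes the Appendix 1 questionnaire as one "which is already administered in routine practice".
- Data Collection names the source of data on enrolled patients (quote cut before its last word): "The electronic medical record and other Penn Medicine secondary databases used to collect data in routine care will be used to collect information on study".
- Subject Recruitment and Screening finds patients by weekly queries of treatment plans, "identifying patients scheduled to initiate a new line of systemic cancer therapy in the following week". Neither this section nor the eligibility criteria require an earlier visit or an earlier questionnaire.
- Background reports that in a large multi-site rollout "mean patient-level adherence was less than 50 percent".

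The Aim 2 patient-level list begins "age, sex, race/ethnicity, education, marital status, cancer type, cancer stage" and continues with insurance. It contains no prior symptom score.

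**The concern.** A baseline covariate earns its place by predicting the outcome. Under randomization, whether it happens to differ between arms is chance and says little about how much residual variance it would remove. A rule that waits for imbalance will therefore drop a strongly prognostic covariate in exactly the trials where it is balanced, although it would still narrow the confidence interval there.

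For symptom burden the natural covariate is the patient's own earlier score on the same 0-4 items. Patients may have any solid tumour and be starting any line of treatment, so their starting symptom levels are likely to vary widely. The outcome is also seen only in patients who complete questionnaires, so fewer than the roughly 160 per arm (480/3) will contribute. Leaving baseline variation in the residual makes a real symptom difference easier to miss, including in the Arm 2 versus Arm 1 comparison.

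**Working it through.** **The plan's own figure.** There is none for symptom burden: no SD, detectable difference or power. The 80% power in Power and Sample Size is for adherence (14.5 points, SD 0.40, two-sided 0.05) and is not used here. For completeness, a plain comparison of two means with those inputs gives 72.7% at 100 per arm and 90.0% at 160 per arm. That neither supports nor weakens this point.

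**Inputs.** From the documents: two-sided alpha 0.05, 1:1:1 allocation, about 480 patients. Assumed, because the documents do not give them:

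- rho, the correlation between the pre-randomization and follow-up scores: 0.3, 0.5, 0.7
- f, the share of analysed patients with a prior score: 0.3 to 0.9
- a starting point of 80% power without adjustment

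**Formula.** With a missing-baseline indicator, residual variance is multiplied by about 1 - f x rho². An effect detectable with 80% power unadjusted lies 1.960 + 0.842 = 2.802 standard errors from zero, so

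adjusted power = Phi(2.802 / sqrt(1 - f x rho²) - 1.960).

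Example, rho 0.5 and f 0.5: 1 - 0.5 x 0.25 = 0.875; 2.802 / sqrt(0.875) = 2.995; Phi(1.035) = 85.0%.

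| rho | f = 0.3 | f = 0.5 | f = 0.7 | f = 0.9 |
|---|---|---|---|---|
| 0.3 | 81.1% | 81.8% | 82.5% | 83.2% |
| 0.5 | 83.0% | 85.0% | 87.0% | 88.9% |
| 0.7 | 85.9% | 89.7% | 93.3% | 96.3% |

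At rho 0.5, the gain equals about 14% more patients at f 0.5 (1/0.875 = 1.143) and 21% more at f 0.7 (1/0.825 = 1.212).

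**Simulation check** (6,000 trials per setting, rho 0.5, missing-indicator model):

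| Patients per arm | f | Unadjusted | Adjusted | Gain (points) |
|---|---|---|---|---|
| 80 | 0.5 | 80.6% | 85.4% | 4.8 |
| 80 | 0.7 | 80.3% | 86.6% | 6.3 |
| 120 | 0.5 | 79.9% | 84.2% | 4.3 |
| 120 | 0.7 | 80.6% | 87.1% | 6.5 |

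The formula is a fair approximation.

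**In SD units.** The difference detectable at 80% power is 2.802 x sqrt(2/n). With 160 per arm all observed it is 0.313 SD. With f 0.5 it falls to 0.306, 0.293 or 0.272 SD at rho 0.3, 0.5 or 0.7. If only half of patients gave a follow-up score (assumption; 80 per arm), it is 0.443 SD unadjusted and 0.443 x sqrt(0.875) = 0.414 SD at rho 0.5, f 0.5.

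**How the adjustment is done matters.** Restricting to patients who have a baseline multiplies variance by (1 - rho²)/f. At f 0.5 this is 1.82, 1.50 or 1.02 for rho 0.3, 0.5 or 0.7. Precision is lost unless rho exceeds sqrt(0.5) = 0.71.

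**The case against.** *Prior scores may be scarce.* A reader might infer that every patient already has a baseline score on file. The documents do not support that. They show routine administration, with completion below 50% and no scheduled baseline questionnaire. Patients are picked up the week before treatment, so the questionnaire tied to the first treatment visit may fall after randomization and could not be used. This stands, and is why f is varied. One consideration pulls the other way: f is the share among patients who supply follow-up scores, and completion looks persistent. A mean of 0.50, SD 0.40 and about 3 opportunities imply an intraclass correlation of (0.16 x 3/0.25 - 1)/2 = 0.46. If that persistence reached back before randomization (assumption), someone who completes a follow-up questionnaire would have completed a given earlier one with probability 0.5 + 0.46 x 0.5 = 0.73. Patients new to the practice lower f, and their number is not given.

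*The plan does not exclude a baseline score.* Correct. Covariates are not enumerated, and the Aim 2 list is not an Aim 1 adjustment set. A score could enter if it were extracted and found unbalanced. What remains is that nothing provides for extracting it, and a balanced score would be left out.

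*The size is assumed.* Also correct. A reader might infer from the table a dependable gain of five points or more once rho and f reach 0.5. At that boundary the formula gives 4.98 points and the simulation 4.3 to 4.8. At rho 0.3 the gain is only 1 to 3 points. Low rho is plausible for single items with 7-day recall, scored before a new regimen and compared with scores during it.

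*Selection is the larger problem.* Scores exist only for completers, completion is what the arms are meant to change, and Arm 3 is weekly while Arms 1 and 2 follow encounters. Reminders might also draw in patients who had not completed before, so f could differ by arm, which the formula does not model. This limits what the adjustment can claim but does not defeat it: conditioning on a pre-randomization variable drops no analysed patient and is not expected to worsen the selection.

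**Conclusion.** The point holds as an inexpensive gain in precision for one of four secondary effectiveness outcomes. It is not an error or a source of bias in the plan, and it leaves the adherence analysis untouched. Entering a pre-randomization score regardless of balance is better than entering it only when unbalanced.

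The size cannot be fixed from the documents. From a hypothetical 80%, power rises by roughly 1 to 3 points at rho 0.3, 3 to 9 at rho 0.5 and 6 to 16 at rho 0.7 as f goes from 0.3 to 0.9. This assumes a linear model, the same f in both arms, and prior-score availability unrelated to outcome.

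A reader might also infer that baseline adjustment would make the symptom comparison unbiased. It would not: selection through arm-dependent completion remains.

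**What to change.** In the Statistical Analysis section for Aim 1, add wording for symptom burden, covering the composite and each item, along these lines:

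- The linear model includes the patient's most recent score on the same item or composite recorded before randomization, within a fixed look-back (for example 90 days), where available.
- A missing prior score is set to a constant and a missing-baseline indicator is included, so that no patient is dropped.
- Both terms enter regardless of observed balance.
- No questionnaire completed after randomization serves as baseline, because arm can affect its completion.

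Add the pre-randomization score to the data extract, and settle the wording before symptom scores are compared by arm. When the outcome is reported, give the share of analysed patients with a prior score by arm, and say that adjustment improves precision but does not remove selection among completers.

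The cost is one more field from the same record system and a few sentences of analysis text, with no new visits, patients or staff. The downside is two extra model terms per outcome, and little gain if few prior scores exist.
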